7.5 HANDLING OF MISSING DATA

7.5.1 Safety

It is not planned to impute missing values for safety parameters.

7.5.2 Pharmacokinetics

Handling of missing PK data will be performed according to the relevant BI internal procedures.

PK parameters that cannot be reasonably calculated based on the available drug concentration-time data will not be imputed.

7.6 RANDOMISATION

Subjects will be randomised to one of the 2 treatment sequences in a 1:1 ratio. The block size will be documented in the CTR.

The sponsor will arrange for the randomisation as well as packaging and labelling of trial medication. The randomisation list will be generated using a validated system that uses a pseudo-random number generator and a supplied seed number so that the resulting allocation is both reproducible and non-predictable.

The randomisation list will contain additional blocks to allow for subject replacement (refer to Section 3.3.5).

7.7 DETERMINATION OF SAMPLE SIZE

There is limited knowledge about the intra-individual variability of the primary endpoints. Previous trials in healthy volunteers (135.57 and 135.67) with TPA-02 were performed as a parallel design and reported a total variability (gCV) of 20.8% and 12%, respectively (both AUC and C_{max} had similar variability). Another trial in rabbits ([n00267264](#)) with TPA-02 and TPA-05 that has been performed as a crossover trial reported an intra-individual variability of approximately 15%. This latter trial observed a gMean ratio of about 100% for C_{max} and 109% for AUC. Therefore, in lack of further evidence it is assumed that the gMean ratio ranges between 100% and 109%.

All calculations below are based on the specifications given in Section [7.2](#). Particularly, a weight of 0.8 for the inverse normal approach, a sample size n₂ for stage 2 between 4 and 42 and usage of the observed gCV and gMean ratio are assumed. Using a sample size of n₁ = 18 subjects for the first stage, the probability to conclude bioequivalence after the first stage is 79% and the overall power to conclude bioequivalence is at least 95%, assuming an intra-individual gCV of 15% and a treatment difference of 9% (ratio scale) (Table [7.7: 1](#)). In order to investigate the sensitivity of the sample size, a range of gCVs around 15% and a range of gMean ratios around 109% are presented.

Table 7.7: 1

Power for concluding bioequivalence overall, power for concluding bioequivalence after stage 1 and average sample size (acceptance range 80-125%) based on an intra-individual geometric coefficient of variation around 15% and for expected ratios of geometric means (test/reference) around 109% in a two-stage 2x2 crossover trial (n₁ = 18)

gCV [%]	Ratio T/R [%]		
	104	109	114
10	>99; >99; 18.0	98.5; 98.2; 18.0	95.3; 79.4; 22.2
15	97.3; 95.4; 18.3	95.2; 79.0; 22.4	83.0; 48.3; 35.8
20	95.5; 77.3; 22.9	89.2; 56.1; 32.1	61.8; 31.6; 43.8

From the above table, even with such variations in assumptions the power is considered to be sufficient to meet the study objectives. The calculations were performed as described by Maurer et al. [[R19-3175](#)] using the function *power.tsd.in* of the R package Power2Stage Version 0.5.2 in R Version 3.6.1.

8 INFORMED CONSENT, TRIAL RECORDS, DATA PROTECTION, PUBLICATION POLICY, AND ADMINISTRATIVE STRUCTURE

The trial will be carried out in compliance with the protocol, the ethical principles laid down in the Declaration of Helsinki, in accordance with the ICH Harmonized Guideline for Good Clinical Practice (GCP), relevant BI Standard Operating Procedures (SOPs), the EU regulation 536/2014, and other relevant regulations. Investigators and site staff must adhere to these principles.

Standard medical care (prophylactic, diagnostic, and therapeutic procedures) remains the responsibility of the subject's treating physician.

The investigator will inform the sponsor immediately of any urgent safety measures taken to protect the trial subjects against any immediate hazard, as well as of any serious breaches of the protocol or of ICH GCP.

Within 1 year after trial termination the Sponsor will submit a summary of the trial report covering all relevant results of the trial to the Competent Authority and to the Independent Ethics Committee.

The Boehringer Ingelheim transparency and publication policy can be found on the following web page: trials.boehringer-ingelheim.com. As a general rule, no trial results should be published prior to archiving of the CTR.

The terms and conditions of the insurance coverage are made available to the investigator and the subjects, and are stored in the ISF.

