Stage 1 (Part B) will comprise $n_1 = 18$ subjects. After the first stage, recruitment will be stopped and an assessment for bioequivalence will be performed. Based on unblinded data from the first stage it will be evaluated whether the trial continues to stage 2 or not. If the confidence intervals for the comparison of Test vs. Reference of all primary and secondary endpoints are within the pre-specified boundaries 80.00% to 125.00%, the trial will be closed after stage 1 due to proven bioequivalence. If bioequivalence is not shown for all endpoints, then a decision regarding continuation of the trial will be made. A sample size re-estimation based on the unblinded data from the first stage will be performed to calculate the number of subjects required for the second stage (Part B) of the trial (n_2). For the sample size re-estimation it is planned to use the observed variability (geometric coefficient of variation, gCV) and the observed geometric mean ratio (GMR) from the (unblinded) stage 1 data. For a more detailed description, please refer to Section [7](#).

An overview of all relevant trial activities is provided in the [Flow Chart](#). For visit schedule and details of trial procedures at selected visits, refer to Sections [6.1](#) and [6.2](#), respectively.

[figure not shown]
A schematic diagram of the trial design is displayed on the following pages.

Proprietary confidential information © 2021 Boehringer Ingelheim International GmbH or one or more of its affiliated companies

[figure not shown]
Figure 3.1: Schedule of stage 1 of

this trial

Screening

[figure not shown]

Period 1, Day 1

[figure not shown]
TPA-02 or TPA-05

Period 2, Day 1

[figure not shown]
TPA-05 or TPA-02

Follow-up

Interim analysis: Performance of stage 2 necessary?

Figure 3.2: Schedule of stage 2 of this trial

Proprietary confidential information © 2021 Boehringer Ingelheim International GmbH or one or more of its affiliated companies

After the first 2 cohorts (planned sample size is N=3 for each cohort) a documented safety review meeting will take place to check whether an activation of coagulation occurred after start of alteplase infusion. The minimum data set for this safety review meeting consists of the following:

- AEs (Note: AEs may be ongoing at the time of the meeting and AE information may be subject to change prior to Database Lock)
- Results from safety lab
- Results from TAT, D-dimer and F1+2

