Although there are multiple primary endpoints, an alpha adjustment with respect to multiple endpoints is not needed because it is required that all primary and secondary endpoints are significant (either at interim or at the final stage, see Section 7.3). The alpha level for the significance testing will be adjusted for considering multiple stages (i.e. looks). The standard inverse normal combination test as described in [R19-3175] with pre-specified weights of \sqrt{w} and $\sqrt{1-w}$ for stage 1 and stage 2, respectively, will be used. The alpha spent for the first stage is fixed to 0.03585 (one-sided) and a user-defined alpha spending function [R10-2517] will be used such that the full level of 0.05 is spent at the final analysis. The information fraction w will be calculated as $w = 0.8 \cdot n_1^*/n_1$, where $n_1 = 18$ and n_1^* is the actual number of subjects contributing at least one evaluable PK parameter for at least one study period (i.e. are in the PKS, see Section 7.3) at the time of the interim analysis. Thus, the ratio n_1^*/n_1 accounts for example for subjects that drop-out early or do not provide evaluable PK parameters for any of the periods. It is expected that $n_1^* = n_1$ and therefore the planning values are $w = 0.8$ and $\alpha_1 = \alpha_2 = 0.03585$; these alpha values correspond to Pocock boundaries. For illustration purposes the following table provides examples on how the adjusted alpha value α_2 and the critical value (see below) will look like depending on different values of n_1^* .

Table 7.2: 1 Information fraction, adjusted alpha level and critical value for stage two depending on different values of n_1^* .

n_1^*	w	α_2	c_2
17	0.75556	0.03359	1.83050
16	0.71111	0.03159	1.85797
15	0.66667	0.02980	1.88381

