7.3.1 Primary endpoint analyses

Primary analysis

The statistical model used for the analysis of the primary endpoints for each stage of the trial will be an analysis of variance (ANOVA) model on the logarithmic scale. That is, the PK endpoints will be log-transformed (natural logarithm) prior to fitting the ANOVA model. This model will include effects accounting for the following sources of variation: sequence, subjects within sequences, period and treatment. All effects will be considered as fixed. The model is described by the following equation:

$$y_{ijkm} = \mu + \zeta_i + s_{im} + \pi_j + \tau_k + e_{ijkm}, \text{ where}$$

y_{ijkm} = logarithm of response measured on subject m in sequence i receiving treatment k in period j,

μ = the overall mean,

Proprietary confidential information © 2021 Boehringer Ingelheim International GmbH or one or more of its affiliated companies

ζ_i = the i^{th} sequence effect, $i = 1, 2$,

s_{im} = the effect associated with the m^{th} subject in the i^{th} sequence,
 $m = 1, 2, \dots, n_i$

π_j = the j^{th} period effect, $j = 1, 2$,

[figure not shown]
τ_k = the k^{th} treatment effect, $k = 1, 2$,

e_{ijkm} = the random error associated with the m^{th} subject in sequence i who received treatment k in period j .

where $e_{ijkm} \sim N(0, \sigma_W^2)$ i.i.d. Note that each stage will be analyzed separately based on data from only this stage, see Section [7.2](#).

Point estimates for the ratios of the geometric means (test/reference) for the primary endpoints (see Section [2.1](#)) and their two-sided confidence intervals (CIs) will be provided. At stage 1, the $(1 - 2\alpha_1) * 100\%$ confidence interval for the gMean ratio will be calculated. If the study continues to stage 2, the repeated confidence interval corresponding to the test decision will be calculated, in conjunction with the median unbiased point estimate as estimate for the final adjusted geometric mean ratio.

Bioequivalence is considered established if the confidence intervals of the geometric means for the primary endpoints are contained in the pre-defined acceptance range, see Section [7.2](#).

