7.4 INTERIM ANALYSES

Part A:

The study was stopped for safety reasons and PK-data from Part A cannot be used for assessment of bioequivalence. Therefore, all analysis were only considered descriptively.

Part B

Blinded review of PK-data

After the first 2 cohorts a blinded review of PK-data will be performed. If these data indicate non-reliable concentration-time profiles (data do not reflect systemic alteplase concentrations due to methodological problems, as it has been observed in Part A), the trial will be discontinued (see [3.3.4.3](#)).

Review of biomarkers

Biomarkers (see [2.2.2.2](#)) can be assessed at any time point during the trial. After the first two cohorts a safety review meeting is planned (see [3.1](#)) to check whether an activation of coagulation could be observed.

Neither the PK review nor the biomarker review will influence the sample size planning of the study. Both, PK and biomarker review are not part of the adaptive design.

Two stage design with formal interim analysis:

After $n_1 = 18$ subjects have completed their crossover (Part B), recruitment will be stopped and an assessment for bioequivalence will be performed. Based on unblinded data from the first stage it will be evaluated whether the trial continues to stage 2 (Part B) or not. This analysis will be performed in an unblinded manner and will be conducted by the trial team. As described in Section [7.2](#), the p-values based on stage 1 (Part B) data are planned to be compared to the value 0.03585.

Equivalently, if the corresponding (adjusted) confidence intervals for the comparison of the primary and secondary endpoints are within the pre-specified boundaries 80.00% to 125.00% (original scale), the trial will be closed after stage 1 (Part B) due to proven bioequivalence. If bioequivalence is not shown for all primary and secondary endpoints, then a decision regarding continuation of the trial will be made by the Principal Investigator, the Trial Statistician, and the Clinical Trial Lead or their respective designees.

The power of the TOST procedure based on the first stage data will be calculated (using the planned treatment effect, the observed variability and the adjusted alpha level for stage 1). If this power is greater or equal to 0.9, the trial is recommended to stop for futility, cf. [\[R19-3175\]](#). Note that this futility rule is considered nonbinding. Note also that there will be no

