Proprietary confidential information © 2021 Boehringer Ingelheim International GmbH or one or more of its affiliated companies

futility criterion with respect to the confidence interval of the gMean ratio after stage 1, in contrast to the proposed algorithm in [R19-3175]. Otherwise a sample size re-estimation (SSR) based on the unblinded data from the first stage will be performed and the trial continues to stage 2 (Part B).

The SSR will be based on the conditional power as described in [R19-3175], i.e. it will use the conditional error rates as well as the estimated conditional target power for the second stage. For the SSR it is planned to use the observed variability (gCV) and the observed geometric mean ratio (GMR) from the (unblinded) stage 1 data. The overall target power to declare bioequivalence at the end of the trial is planned to be 90%. Note that a specific power adjustment due to multiple endpoints will not be done [R17-0365] and the sample size recalculation, if required, will be based on observed results from primary and secondary PK parameters. The calculation will be performed for each parameter and the highest sample size will be used. Note that the minimum sample size for stage 2 is set to 4, as done and recommended in [R19-3175]. Moreover, for this study a maximum overall sample size of 72 will be considered. Therefore, the number of subjects in stage 2 will not exceed 42, even if the calculated sample size based on stage 1 data is higher than 42.

If bioequivalence is shown for one endpoint but not the other(s), only the endpoint(s) where bioequivalence has not been shown will be tested a second time at the end of the trial [R17-1639]. Note, however, that for completeness all PK parameters and corresponding confidence intervals for the comparison(s) as described in Section 7.3.1 and Section 7.3.2 will be calculated.

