7.4 PRIMARY ENDPOINT

7.4.1 Primary analysis of the primary endpoint

The statistical model used for the analysis of the primary endpoints for each stage of the trial will be an analysis of variance (ANOVA) model on the logarithmic scale as described in the CTP, section 7.3.1.

Each stage will be analyzed separately based on data from only this stage, see CTP Section 7.2.

Stage 1 analysis

After stage 1, an assessment for bioequivalence will be performed. Data of stage one will be analyzed with the statistical model described in the **CTP, section 7.3.1**.

CTP section 7.3.1 *Point estimates for the ratios of the geometric means (test/reference) for the primary endpoints (see Section 2.1) and their two-sided confidence intervals (CIs) will be provided. At stage 1, the $(1 - 2\alpha_1) * 100\%$ confidence interval for the gMean ratio will be calculated.*

The alpha spent for the first stage is fixed to 0.03585 (one-sided), see **CTP section 7.2**.

The analysis of stage 1 data will be implemented using SAS PROC MIXED:

```
PROC MIXED DATA=pks_stage1;
  CLASS subject treatment(ref==TPA-02=) sequence period;
  MODEL logkp = treatment sequence period subject / DDFM=KR;
  LSMEANS treatment / PDIFF CL ALPHA=0.0717;
  RUN;
```

Bioequivalence is concluded, if the corresponding (adjusted) confidence intervals for the comparison of the primary and secondary (same model, see CTP section 7.5.2) endpoints are within the pre-specified boundaries 80.00% to 125.00% (original scale).

1 A) If bioequivalence is shown, the trial will be closed after stage 1.

1 B) If bioequivalence is not shown for all primary and secondary endpoints after stage 1, then a decision regarding continuation of the trial will be made by the Principal Investigator, the Trial Statistician, and the Clinical Trial Lead or their respective designees.

As stated in the CTP, for all endpoints not meeting the bioequivalence criterion, the following calculations will be performed.

The power of the TOST procedure based on the first stage data will be calculated (using the planned treatment effect, the observed variability and the adjusted alpha level for stage 1). If this power is greater or equal to 0.9, the trial is recommended to stop for futility, cf. (11) Note that this futility rule is considered nonbinding.

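### Section 7.7 presents one-endpoint power (79% after stage 1, at least 95% overall) as the probability of concluding bioequivalence, which needs all three endpoints to pass

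*Protocol*

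**What the plan says.** Section 7.7 of the protocol takes one gCV (15%) and one ratio (109%), names no endpoint, and reports that "the probability to conclude bioequivalence after the first stage is 79% and the overall power to conclude bioequivalence is at least 95" (per cent). Table 7.7: 1 gives that cell as 95.2% overall, 79.0% after stage 1 and an average of 22.4 subjects, and its caption also speaks of concluding bioequivalence. From the table the section concludes that "even with such variations in assumptions the power is considered to be sufficient to meet the study objectives".

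Section 7.7 bases its calculations on Section 7.2, where "it is required that all primary and secondary endpoints are significant". Section 3.1 closes the trial after stage 1 only if the intervals for "all primary and secondary endpoints are within the pre-specified boundaries 80.00% to 125.00" (per cent). Protocol Section 7.4 and SAP Section 7.4.1 apply the same rule.

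Two other statements bear on the point. Section 7.4, in the text on sample size re-estimation, says that "a specific power adjustment due to multiple endpoints will not be done". Section 7.3.1 words success more narrowly: "Bioequivalence is considered established if the confidence intervals of the geometric means for the primary endpoints are contained in the pre-defined acceptance range".

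**The concern.** The planned event is that three endpoints pass, and a joint event cannot be more probable than any one of its parts. If 79% is the chance that one endpoint passes at stage 1, the chance that the trial stops there with bioequivalence shown is at most 79%, and lower unless the endpoints always pass or fail together.

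The table is the only support for the statement that power is sufficient when the assumptions vary. The stage 1 figure also tells sponsor and ethics committee how likely it is that up to 42 more healthy men will have to be dosed.

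**Working it through.** **Inputs from the documents.** n1 = 18; one-sided stage 1 alpha 0.03585; weight w = 0.8; c2 = 1.80107 (Section 7.2). Stage 2 size 4 to 42; 90% target power; stop recommended if stage 1 power at the planned effect is 0.9 or more; only failing endpoints retested; largest n2 over parameters used (Section 7.4). gCV and ratios from Section 7.7, including the rabbit crossover result of about 100% for Cmax and 109% for AUC.

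**Step 1: reproduce the stage 1 figure with one endpoint.** At gCV 15%:
- σ = √ln(1 + 0.15²) = 0.1492
- SE = σ√(2/18) = 0.0497, with 16 df; t(1 − 0.03585; 16) = 1.929
- distance to the upper limit: (ln 1.25 − ln 1.09)/SE = (0.2231 − 0.0862)/0.0497 = 2.75
- distance to the lower limit: (0.2231 + 0.0862)/0.0497 = 6.22
- exact TOST power: **79.1%** (stated 79.0%)

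The same calculation gives 56.2% at 20%/109% (stated 56.1%), 98.6% at 15%/100% and 83.9% at 20%/100%.

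**Step 2: reproduce the two-stage figures with one endpoint.** The final test is √0.8·Φ⁻¹(1 − p1j) + √0.2·Φ⁻¹(1 − p2j) ≥ 1.80107 for j = 1, 2. Simulating 80,000 trials gives, as overall; stage 1; average N:
- 15%/109%: 95.3; 79.1; 22.4 (stated 95.2; 79.0; 22.4)
- 20%/109%: 89.3; 56.0; 32.1 (stated 89.2; 56.1; 32.1)

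All nine cells of the table reproduce within 1 point with one endpoint.

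**Step 3: what follows without assuming a correlation.** At gCV 15% with all three endpoints at 109%, the stage 1 joint probability lies between 1 − 3 × 20.9% = 37.3% and 79.1%. Three independent endpoints would give 0.791³ = 49.5%. Overall power has no such simple bound, because n2 is set by the worst endpoint and the futility stop depends on how endpoints are combined.

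**Step 4: joint simulation.** Success means that all three endpoints pass, n2 is the largest need among failing endpoints, and only failing endpoints are retested. Runs had 20,000 to 40,000 trials per setting. Assumed, because the documents are silent: AUC-AUC residual correlation 0.98-0.995, Cmax-AUC 0.3-0.9, and the same gCV for every endpoint. The futility stop was handled in three ways, because "Note that this futility rule is considered nonbinding" and the SAP says only that "for all endpoints not meeting the bioequivalence criterion, the following calculations will be performed", without saying how several failing endpoints combine.

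| gCV; ratios | Stage 1 | Overall: stop if any failing endpoint meets the rule | Overall: stop only if all do | Overall: rule not followed |
|---|---|---|---|---|
| 15%; AUC 109, Cmax 100 | 75-78% | 94-95% | 95-96% | 95-97% |
| 15%; all 109 | 63-73% | 91-93% | 92-95% | 93-97% |
| 20%; AUC 109, Cmax 100 | 44-47% | 86-89% | within 1 point | within 1 point |
| 20%; all 109 | 34-48% | 81-86% | within 1 point | within 1 point |

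When the rule is not followed, one endpoint alone reaches 96-97% at 15%/109%, so the last column should be compared with that figure and not with 95.2%.

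**Step 5: the narrower rule in Section 7.3.1.** With AUC0-tz and Cmax only, stage 1 at gCV 15% is 78-79% (AUC 109%, Cmax 100%) or 65-74% (both 109%).

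**The case against.** Every number in the table is correct for what was computed. Section 7.4 discloses that power is not adjusted for multiple endpoints, Section 7.7 names the software function, and each cell carries one gCV and one ratio, so a statistician could infer a one-endpoint calculation. Under the ratios seen in rabbits the gap at gCV 15% is about 1 to 4 points at stage 1 and at most about 1 point overall. At gCV 20% with those ratios the overall loss is also small: most runs put it between about 0.4 and 3 points, and one setting (AUC correlation 0.995, Cmax-AUC 0.3, rule not followed) showed none. The larger losses need Cmax at 109% as well, and every all-endpoint figure rests on assumed correlations. Stage 2 is sized from observed data in any case.

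Most of this stands, and it limits the weight of the point. It does not remove it. The note in Section 7.4 concerns re-estimation and does not tell a reader of Section 7.7 that the figures are per endpoint. Choosing not to adjust is legitimate, but the result still has to be named for what it is. Cmax at 109% lies within the 100-109% range that Section 7.7 itself assumes.

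**Conclusion.** The concern holds as a labelling error in a power statement on which the protocol relies. The 79% and 95.2% are one-endpoint figures; the success rule covers three.

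At gCV 15% the stage 1 probability falls by 1 to 4 points with Cmax at 100% and by 6 to 16 points with all endpoints at 109%. Overall power stays above 90% across the assumed correlations; only the extreme of three independent endpoints, all at 109%, fell below it, to about 88%. The trial is therefore not shown to be underpowered at its planning gCV.

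At gCV 20% and 109%, stage 1 is clearly lower than the stated 56.1%. Overall power is slightly below 89.2% if Cmax is at 100%, and 3 to 8 points below it if Cmax is also at 109%.

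The direction at stage 1 needs no assumption. The sizes depend on the assumed correlations, the common gCV and the futility handling. This is a minor point that is cheap to correct.

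**What to change.** - In Section 7.7 and the caption of Table 7.7: 1, label the power figures as per endpoint.
- Add simulated all-endpoint figures for the gCV 15% and 20% rows, as a range. State the ratio assumed for each endpoint, the correlation range, and how the futility stop is combined when more than one endpoint fails.
- Reconcile Section 7.3.1 (primary endpoints) with Sections 3.1, 7.2 and 7.4 (primary and secondary), so that the power refers to one defined event.

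The cost is a label, a sentence, one simulation and a somewhat less favourable stated power. The sample size and the test procedure stay as they are.

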Clinical Trial Protocol

Document Number:		c30603221-08
EudraCT No.	2019-004932-40	
EU Trial No.	NA	
BI Trial No.	0135-0340	
BI Investigational Medicinal Product	alteplase (TPA-05, 50 mg/vial and TPA-02, 50 mg/vial)	
Title	Bioequivalence of alteplase derived from two different manufacturing processes following intravenous administration in healthy male volunteers	
Lay Title	A study in healthy men to compare 2 different formulations of alteplase	
Clinical Phase	I	
Clinical Trial Leader	
Phone: [REDACTED] Fax: [REDACTED]
	
Investigator	
Phone: [REDACTED] Fax: [REDACTED]
	
Status	Final Protocol (Revised Protocol (based on global amendment 7))	
Version and Date	Version: 8.0	Date: 14 April 2021
Page 1 of 98		

Proprietary confidential information © 2021 Boehringer Ingelheim International GmbH or one or more of its affiliated companies. All rights reserved. This document may not - in full or in part - be passed on, reproduced, published or otherwise used without prior written permission
		

CLINICAL TRIAL PROTOCOL SYNOPSIS

Company name	Boehringer Ingelheim
Protocol date	17 February 2020
Revision date	14 April 2021
BI trial number	0135-0340
Title of trial	Bioequivalence of alteplase derived from two different manufacturing processes following intravenous administration in healthy male volunteers
Investigator:	[REDACTED]
Trial site	[REDACTED]
Clinical phase	I
Trial rationale	To allow a change of manufacturing process of alteplase (new process: TPA-05)
Trial objective	To establish the bioequivalence of alteplase derived from two different manufacturing processes (new process, TPA-05, vs. current process, TPA-02)
Trial design	open-label, randomised, 2-way cross-over design with at least 24 h wash-out
Trial endpoints:	Primary endpoints: AUC_{0-tz} and C_{max} Secondary endpoints: $AUC_{0-\infty}$
Number of subjects	
total entered 72
 
each treatment 72
 
The trial part A was performed with 12 subjects and resulted in PK-data that cannot be used for the assessment of bioequivalence. Therefore part B of this trial will be performed following a 2-stage design with an adaptive sample size re-estimation. Initially 18 subject will be dosed (stage 1, Part B). After an interim analysis a maximum of 42 subjects may be dosed in stage 2 (Part B).

Diagnosis	Not applicable
Main criteria for inclusion	Healthy male subjects, age of 18 to 45 years (inclusive), body mass index (BMI) of 18.5 to 29.9 kg/m ² (inclusive)

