The SSR will be based on the conditional power as described in (11), i.e. it will use the conditional error rates as well as the estimated conditional target power for the second stage. For the SSR it is planned to use the observed variability (gCV) and the observed geometric mean ratio (GMR) from the (unblinded) stage 1 data. Note that a specific power adjustment due to multiple endpoints will not be done and the sample size recalculation, if required, will be based on observed results from primary and secondary PK parameters. The calculation will be performed for each parameter and the highest sample size will be used. Note that the minimum sample size for stage 2 is set to 4, as done and recommended in (11). Moreover, for this study a maximum overall sample size of 60 will be considered.

This step may be implemented using function `interim.tsd.in` from the R package `Power2Stage`:

```
interim.tsd.in(weight = 0.8, max.comb.test = FALSE, targetpower =  
0.9,  
                 GMR1 = GMR1, CV1 = CV1, n1 = n1, ,  
                 GMR = 1.09, usePE = TRUE, max.n = 60, fCrit = "No")
```

For GMR1 and CV1 it is planned to use the observed results from stage 1, i.e. the gMean ratio and gCV as derived from the above proc mixed call. Similarly, df1 and SEM1 are the degrees of freedom and standard error of the difference of LSmeans, respectively, and are to be taken (on the log-scale) from the same proc mixed call. n1 is the number of subjects in the PKS from stage 1,

Note that the weight of 0.8 may be adjusted as described in the CTP Section 7.2.

If applicable, Stage 2 analysis

Step 2 A)

Data of stage two will be analyzed with the same statistical model described in the CTP, section 7.3.1 using in principle the same SAS dummy code as described above in [Section](#)

[7.4.1](#) of the TSAP. Note again that the input data for the proc mixed call will be PKS data from stage 2 only.

```
PROC MIXED DATA=pkstage2;
  CLASS subject treatment(ref==TPA-02=) sequence period;
  MODEL logkp = treatment sequence period subject / DDFM=KR;
  LSMEANS treatment / PDIFF CL ALPHA=2*alpha2;
RUN;
```

where α_2 is planned to be 0.03585 and may be adjusted based in accordance with the weight.

Step 2 B)

Study success will then be determined based on the standard inverse normal combination test.

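### Table 7.7:1 resets the planned effect to each column's true ratio, while the design fixes it at 1.09, so power at a 114% ratio is overstated by up to 14 points

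*Protocol*

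**What the plan says.** Protocol 7.4 describes the interim step for endpoints that have not shown bioequivalence after stage 1. Stage 1 power is calculated "using the planned treatment effect, the observed variability and the adjusted alpha level for stage 1". If it reaches 0.9, stopping for futility is recommended, but the rule is non-binding. Otherwise stage 2 is sized from conditional error rates and a conditional target power, using the observed gCV and ratio, with an overall target of 90%.

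SAP 7.4.1 repeats this and offers an R call containing "GMR = 1.09, usePE = TRUE, max.n = 60". The planned effect is therefore a constant, 1.09, and the observed ratio is used when stage 2 is sized.

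Protocol 7.7 takes a ratio of 109% and a gCV of 15% as the planning case and presents Table 7.7:1 as a check on sensitivity around those values. Each cell gives overall power, power after stage 1 and average sample size. The cell for gCV 10% and ratio 114% reads "95.3; 79.4; 22.2". The text does not say which planned effect was used in each column. It concludes that "even with such variations in assumptions the power is considered to be sufficient to meet the study objectives".

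**The concern.** A trial has one planned effect, chosen before the true ratio is known. A sensitivity table should hold it fixed and vary only the truth. The cell for gCV 10% and ratio 114% shows that this was not done. At a planned effect of 1.09 and gCV 10%, the table's own stage 1 power is 98.2%, well above the 0.9 threshold, so nearly every trial that fails stage 1 would be recommended to stop. Yet the cell credits stage 2 with 95.3 − 79.4 = 15.9 points of power.

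The table is the only support for the statement that power holds up when the assumptions vary. A ratio above 109% is the direction that endangers the trial. The 109% itself comes from a rabbit study, and Protocol 7.7 concedes that little is known about within-subject variability.

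**Working it through.** **Inputs**
- Stage 1 size n1 = 18 (Protocol synopsis, 3.1).
- Stage 1 one-sided alpha 0.03585 and final critical value c2 = 1.80107 (Protocol 7.2). A check of the Pocock boundary at w = 0.8 gives 0.03585 and 1.801.
- "a weight of 0.8 for the inverse normal approach" (Protocol 7.7), so w = 0.8.
- Stage 2 size from 4 to 42 (Protocol 7.4: "Therefore, the number of subjects in stage 2 will not exceed 42"), so at most 18 + 42 = 60, as in the SAP code.
- Acceptance range 80.00% to 125.00%, target power 0.90, futility threshold 0.9.

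**Rule simulated**
1. Stage 1 succeeds if both one-sided p-values are at most 0.03585.
2. Otherwise compute power1, the stage 1 TOST power at the planned effect and the observed gCV. Stop if power1 ≥ 0.9.
3. Otherwise the conditional target power is 1 − (1 − 0.9)/(1 − power1).
4. The conditional error for each one-sided test is 1 − Φ[(c2 − √w·Φ⁻¹(1 − p1j))/√(1 − w)].
5. Choose the smallest even n2 from 4 to 42 that reaches the conditional target power at the observed ratio and gCV.
6. Apply the inverse normal test with c2.

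Each cell used 60,000 to 100,000 simulated trials. At 80% power and 60,000 trials the standard error is √(0.8 × 0.2/60,000) = 0.16 points.

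**Step 1: reproduce the table.** With the planned effect set to each column's ratio, the eight numeric cells agree within about 0.6 points of power and 0.1 of average N, and the cell given as above 99% comes out at 100%.

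**Step 2: hold the planned effect at 1.09.** Overall power (%), with average N in brackets:

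| gCV / ratio | Stated | Planned = true ratio | Planned = 1.09 | Planned = 1.09, futility ignored |
|---|---|---|---|---|
| 10 / 114 | 95.3 (22.2) | 95.5 (22.1) | 81.6 (18.4) | 89.0 (19.1) |
| 15 / 114 | 83.0 (35.8) | 83.5 (35.8) | 74.4 (30.5) | 76.1 (30.9) |
| 20 / 114 | 61.8 (43.8) | 62.4 (43.9) | 60.2 (42.1) | 60.4 (42.1) |
| 10 / 109 | 98.5 (18.0) | 98.6 (18.0) | 98.6 (18.0) | 99.6 (18.1) |
| 15 / 109 | 95.2 (22.4) | 95.4 (22.3) | 95.4 (22.3) | 96.3 (22.4) |
| 20 / 109 | 89.2 (32.1) | 89.7 (32.0) | 89.7 (32.0) | 89.7 (32.0) |
| 15 / 104 | 97.3 (18.3) | 97.3 (18.3) | 99.5 (18.8) | 99.7 (18.8) |
| 20 / 104 | 95.5 (22.9) | 95.8 (22.8) | 98.8 (24.4) | 98.9 (24.4) |

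Overstatement at 114%:
- Futility followed: 95.3 − 81.6 = 13.7, 83.0 − 74.4 = 8.6 and 61.8 − 60.2 = 1.6 points.
- Futility ignored: 6.3, 6.9 and 1.4 points.

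Understatement at 104%, futility followed: 99.5 − 97.3 = 2.2 and 98.8 − 95.5 = 3.3 points.

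**Step 3: mechanism.** At gCV 10% and ratio 114%, 17.7% of trials meet the futility rule when the planned effect is 1.09, against 2.2% when it is 1.14. Stage 1 fails in 100 − 79.9 = 20.1% of trials, so the rule stops 17.7/20.1 = 88% of the failures.

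The conditional target power also shifts. Taking the table's stage 1 powers at gCV 15%, with the observed gCV equal to the true one:
- Planned 1.09: 1 − 0.1/(1 − 0.790) = 0.52.
- Planned 1.14: 1 − 0.1/(1 − 0.483) = 0.81.

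The lower target gives a smaller stage 2, which is why a gap remains when futility is ignored.

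**Step 4: alternatives.** Three variants with the planned effect at 1.09 were tried: no futility stop with sizing on conditional error alone, the futility stop with sizing on conditional error alone, and the planned ratio in place of the observed one for sizing. None reproduces the table. At gCV 10% and ratio 114% they give 99.2%, 82.2% and 81.1%.

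**The case against.** Every published cell can be reproduced, so the numbers are correct for some scenario. The caption speaks of expected ratios, so each column could show what would follow had that ratio been the planning value. The Protocol mentions only a planned effect; the constant 1.09 comes from SAP code offered as one possible implementation. The futility rule is non-binding, and without it the largest gap is about 7 points. A ratio of 114% lies outside the assumed 100% to 109%, and the 104% column errs on the cautious side. The table already prints 83.0%, 61.8% and 89.2%, all below 90%, and the sponsor still judged power sufficient. Alpha, sample sizes and the primary analysis are untouched.

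Much of this limits the consequence and should be granted: no false claim of bioequivalence can follow, and the base case stands. It does not rescue the table. Section 7.7 presents the columns as sensitivity around a single planning value and never says the plan itself changes, while the SAP supplies one value for one trial. The non-binding status narrows the gap but does not close it. The table itself appears to assume that futility is followed: 98.5% at gCV 10% and ratio 109% matches the run with the stop (98.6%) and not the run without it (99.6%).

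**Conclusion.** The concern holds. The 104% and 114% columns do not describe the design that the Protocol and SAP specify. At 114%, stated overall power is too high by 13.7, 8.6 and 1.6 points for gCV 10%, 15% and 20% if the futility recommendation is followed, and by 6.3, 6.9 and 1.4 points if it is ignored. At 104% the table is too low by 2.2 points (gCV 15%) and 3.3 points (gCV 20%). All three 114% cells fall below the 90% target. Of these, gCV 10% is the one the table shows as met. The cell for gCV 20% and ratio 109% (89.2%) is also just below.

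This rests on a planned effect of 1.09, taken from the SAP code and the planning case in Protocol 7.7, and on a re-implementation of the method, not the named package. The headline 79% and 95% and the stage 1 size of 18 are unaffected. What fails is the sensitivity conclusion.

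**What to change.** Rerun Table 7.7:1 in the package named in Protocol 7.7, with the planned effect fixed at 1.09 and only the true ratio and gCV varied. State that setting in 7.7. Because the futility rule is non-binding, report power with and without the stop.

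Replace the 104% and 114% columns. Expected overall power with the stop, for gCV 10%, 15% and 20%, is about >99%, 99.5% and 98.8% at 104%, and 81.6%, 74.4% and 60.2% at 114%. Average N changes too.

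Reword the conclusion to say that power falls below the 90% target at 114% for every gCV shown, and marginally so at gCV 20% with ratio 109%.

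The cost is one simulation, one table and a few sentences, with no change to trial conduct. The 114% figures become less favourable and the 104% figures slightly more so.
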